Stati	stical Analysis Plan	Pa	ige 1 of 9
Sponsor	Study		Version
Farapulse	FARA-FREE II PMCF Stu	dy	1.1

Farapulse FARA-FREE II PMCF Study

Statistical Analysis Plan
Version DRAFT 07July2020

Stati	stical Analysis Plan	Pa	ge 2 of 9
Sponsor	Study		Version
Farapulse	FARA-FREE II PMCF Stu	dy	1.1

Version History

Version	Version Date	Author/Title	Summary of Key Changes
1.0	<20Aug2020>	[name]	Initial Release
1.1	01Dec2020	[name]	Updated to reflect FARA-Free II reference.

Stati	stical Analysis Plan	Page 3 of	9
Sponsor	Study	Version	
Farapulse	FARA-FREE II PMCF Stu	dy 1	.1

Document Approval

	Document Approval
Author	
Authored By	
Signature	
Date	
Role	
Approval	
Approved By	
Signature	
Date	
Role	
Approval	
Approved By	
Signature	
Date	
Role	
Approval	
Approved By	
Signature	
Date	
Role	
Approval	
Approval Approved By	
Signature	
Date	
Role	

Statistical Analysis Plan Page 4 of 9 Sponsor Study Version Farapulse FARA-FREE II PMCF Study 1.1

Table of Contents

1	Introd	uction	. 5
2	Objec	tives	. 5
:	2.1 I	Endpoints	, 5
	2.1.1	Primary Safety Endpoint	, 5
	2.1.2	Additional Safety Endpoints	. 6
	2.1.3	Primary Effectiveness Endpoint	. 6
	2.1.4	Additional Effectiveness Outcomes	. 7
3	Statist	tical Analyses	. 7
;	3.1 (General Considerations	. 7
	3.1.1	Descriptive Statistics	. 7
	3.1.2	Study Day	. 7
	3.1.3	Visit Windows	8
	3.1.4	Statistical Significance	8
	3.1.5	Precision	8
:	3.2	Analysis Populations	8
:	3.3 I	Demographics and Baseline Characteristics	8
;	3.4	Analysis of Study Endpoints	8
	3.4.1	Primary Safety Endpoint	. 8
	3.4.2	Primary Effectiveness Endpoint	ç
;	3.5	Additional Analyses	ç
	3.5.1	Procedural Outcomes	c

Stati	stical Analysis Plan	Pa	ige 5 of 9
Sponsor	Study		Version
Farapulse	FARA-FREE II PMCF Stu	dy	1.1

1 Introduction

This statistical analysis plan (SAP) describes the planned statistical methods to be used during the reporting and analysis of data collected under the FaraPulse FARA-FREE II PMCF study. Study specific details can be found in the Clinical Investigational Plan.

2 Objectives

The purpose of the study is to provide ongoing post-market demonstration of the safety and effectiveness of the FaraPulse system.

2.1 Endpoints

The following primary endpoints for the demonstration of safety and effectiveness are outlined below.

2.1.1 Primary Safety Endpoint

The primary safety endpoint for this study is the Composite Safety Endpoint (CSE) defined as the incidence of the following serious adverse events (SAEs) which are device- or procedure-related, as adjudicated by the CEDMC based on the definitions contained in the Composite Safety Endpoint Definitions as outlined in the CIP.

Early onset (within 7 days of an index or protocol-specified reablation procedure)

- Death
- Myocardial infarction
- Persistent diaphragmatic paralysis
- Stroke
- Transient ischemic attack
- Peripheral or organ thromboembolism
- Pericardial effusion, hemorrhage or tamponade
- Vascular access complications
- Hospitalization
- Heart block

Late onset (any time during follow-up)

- Pulmonary vein stenosis
- Atrio-esophageal fistula

The proportion will be compare to the performance goal (PG) of 17%. The safety hypotheses are as follows:

 $H_0: \Pi \ge PG$ $H_A: \Pi < PG$

Statistical Analysis Plan		Pa	ge 6 of 9
Sponsor	Study		Version
Farapulse	FARA-FREE II PMCF Stu	dy	1.1

where Π is the proportion of subjects with one or more CSE. The null hypothesis will be rejected in favor of the alternative if the upper bound of the 95% binomial exact confidence limit is less than the PG. Sample size is estimated assuming an underlying CSE rate of 9% compared to the PG of 17%. Assuming 80% power and one-sided Type I error of 2.5%, a minimum sample size of 150 is required.

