PRIMARY SAFETY ENDPOINT:	The primary safety endpoint is the Composite Safety Endpoint (CSE) defined as the proportion of Safety Subjects with one or more of the following device- or procedure-related SAEs as adjudicated by the CEC based on protocol definitions. Early onset (within 7 days of an index or Rescheduled Index procedure: • Death • Myocardial infarction • Persistent phrenic nerve palsy • Stroke • Transient ischemic attack (TIA) • Peripheral or organ thromboembolism • Cardiac tamponade / perforation • Pericarditis • Pulmonary edema • Vascular access complications • Heart block • Gastric motility/pyloric spasm disorders Late onset (any time through the completion of 12 month follow-up visit) • Pulmonary vein stenosis • Atrio-esophageal fistula					
Additional Safety Analyses:	 Severe Ablation Complications Nonserious / Serious CSEs Post-Blanking Direct Current Cardioversions Post-Blanking Arrhythmia Hospitalizations Any Related SAE Any Related Stroke or TIA 					

PRIMARY EFFECTIVENESS ENDPOINT:	 The primary performance endpoint is Treatment Success in Modified Intent-to-Treat (mITT) subjects, defined as: Acute Procedural Success, AND 1. Chronic Success, defined as freedom from: a. At the Index / Rescheduled Index Procedure: Use of a non-PFA treatment modality for PVI b. After the Blanking Period: i. Occurrence of any Detectable AF, AFL or AT (excluding CTI-dependent AFL confirmed by EP study) ii. Cardioversion for AF, AFL or AT (excluding for CTI-dependent AFL) iii. Use of any Type I or Type III antiarrhythmic medication for the treatment of AF, AFL or AT c. At any time: i. Re-ablation for AF, AFL or AT (other than for CTI-dependent AFL)
Additional Effectiveness Analyses:	 Acute Procedural Success Acute Vein Success Chronic Success Chronic Success Allowing Re-ablation Chronic Success Allowing AADs Treatment Success Allowing Re-ablation Treatment Success Allowing AADs Treatment Success with PVI/CTI Only Early Recurrence of AF Rate of Re-ablation AF Symptom Assessment

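### The only SAP supplied is headed FARA-FREE II and prints a different Composite Safety Endpoint from the FARA-FREEDOM synopsis, against the same 9%, 17% and N=150

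*SAP*

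**What the plan says.** **Identity.** The SAP's page headers and Introduction name the FARA-FREE II PMCF study. Its version history ends at 1.1, 01Dec2020, and its cover still carries a draft date of 07July2020. FARA-FREEDOM appears nowhere in it. The other document is the FARA-FREEDOM synopsis, CS1170 Rev D, issued 18 May 2022, which summarises CIP CS1169 Rev D. SAP 2.1.2 also lists a cranial MRI endpoint in a brain imaging subpopulation. The synopsis has no such endpoint; its only MRI belongs to a work-up triggered by suspected stroke.

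**Components.** SAP 2.1.1 includes "Hospitalization" and "Pericardial effusion, hemorrhage or tamponade". The synopsis (Primary Safety Endpoint) has no hospitalization item. It lists "Cardiac tamponade / perforation • Pericarditis • Pulmonary edema" and "Gastric motility/pyloric spasm disorders".

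**Clock for early events.** SAP: "Early onset (within 7 days of an index or protocol-specified reablation procedure". Synopsis: "Early onset (within 7 days of an index or Rescheduled Index procedure".

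**Analysis set.** The synopsis defines the endpoint as "the proportion of Safety Subjects with one or more of the following device- or procedure-related SAEs". SAP 3.4.1.1 puts every ITT subject in the denominator.

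**Decision rule.** Under SAP 3.4.1.1 the endpoint is met if the upper limit of the exact 95% interval lies below 17%. Both documents plan on a 9% rate, one-sided 2.5% error, 80% power and at least 150 subjects. The synopsis enrols about 180 to allow for 15% losses.

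**The concern.** The documents do not say whether FARA-FREE II is this study. If it is a separate study, FARA-FREEDOM has no SAP in the material supplied. If it is this study, an analyst who programs SAP 2.1.1 as printed can count different subjects from those the synopsis defines, on the endpoint that decides the primary safety claim. SAP 3.4.1 refers to the events that follow but lists none, so 2.1.1 is the only list available to program.

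A second issue follows. One expected rate and one performance goal stand beside two different composites. Neither document says which composite they were derived for, so the goal may be calibrated to an endpoint other than the one analysed.

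**Working it through.** **1. The plan's own sample size.** Inputs: null 17%, alternative 9%, one-sided 2.5%, exact binomial (synopsis, Sample Size Considerations; SAP 2.1.1). Take the largest c with P(X ≤ c | n, 0.17) ≤ 0.025; power is P(X ≤ c | n, 0.09). At n=150, c=16: the null probability is 0.0207 (0.0361 at 17) and the power is 80.7%. N=150 is reproduced. Allowing for losses, 150 / 0.85 = 176.5, so 177, consistent with about 180. The arithmetic is sound for a 9% rate; the question is which composite that rate describes.

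**2. The two composites side by side.**

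| Element | SAP 2.1.1 | Synopsis | Can it change the count? |
|---|---|---|---|
| Hospitalization | listed | absent | yes: the SAP can add subjects |
| Pericarditis | absent | listed | yes: the SAP can omit subjects |
| Pulmonary edema | absent | listed | yes: the SAP can omit subjects |
| Gastric motility / pyloric spasm | absent | listed | yes: the SAP can omit subjects |
| Start of 7-day clock | index or reablation | index or rescheduled index | yes: the synopsis provides for re-ablation |
| Pericardial item | effusion, hemorrhage, tamponade | tamponade, perforation | depends on CIP definitions not supplied |
| Late-onset window; committee name | follow-up; CEDMC | through the 12-month visit; CEC | not shown to |
| Denominator | ITT | Safety Subjects, not defined in what was supplied | differs in name; no numerical difference shown |

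The differences work in opposite directions. Hospitalization may also recapture some subjects whose pericarditis, pulmonary edema or gastric event the SAP does not list.

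**3. Where the rule turns.** The two-sided 95% Clopper-Pearson upper limit for x events in n is the 0.975 quantile of Beta(x+1, n−x).

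| n | Source | Largest passing count | Upper limit | One more event | Expected events at 9% |
|---|---|---|---|---|---|
| 180 | planned enrolment | 20 | 16.64% | 17.28%, fails | 16.2 |
| 153 | 180 × 0.85 | 16 | 16.43% | 17.19%, fails | 13.8 |
| 150 | stated minimum | 16 | 16.74% | 17.52%, fails | 13.5 |

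**4. Chance that the choice of list reverses the result.** Assume a true rate of 9% under one list, X ~ Bin(n, 0.09), and a fixed net difference of k subjects under the other. With c the largest passing count:

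- a gain of k turns a pass into a fail with probability P(c−k+1 ≤ X ≤ c);
- a loss of k turns a fail into a pass with probability P(c+1 ≤ X ≤ c+k).

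At n=180, c=20, the probabilities of 18, 19, 20, 21, 22 and 23 events are 8.87%, 7.48%, 5.95%, 4.49%, 3.21% and 2.18%. For k=3, pass to fail is 8.87 + 7.48 + 5.95 = 22.30%, and fail to pass is 4.49 + 3.21 + 2.18, which is 9.87% before rounding of the terms.

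| n | Pass to fail, k=1 | k=3 | Fail to pass, k=1 | k=3 |
|---|---|---|---|---|
| 180 | 5.95% | 22.30% | 4.49% | 9.87% |
| 153 | 8.67% | 29.94% | 6.91% | 15.71% |
| 150 | 8.25% | 29.15% | 6.43% | 14.35% |

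The values of k are assumptions. The documents give no component rates from which to estimate them.

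**The case against.** **It may be another study's SAP.** Then the two texts do not contradict each other, and what remains is a gap in the material supplied, not a shown error in the plan. This stands as a limit. The matching 9%, 17% and 150, and the matching 65%, 50% and 85 for effectiveness, suggest a common origin but do not prove that the studies are the same. Either way the sponsor must identify the governing SAP.

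**The CIP governs.** The SAP says events are adjudicated "based on the definitions contained in the Composite Safety Endpoint Definitions as outlined in the CIP", and that plan was not supplied. It could settle what counts as hospitalization, as a protocol-specified reablation or as a pericardial event, so the pericardial wording is left open here. But a set of event definitions does not remove an item from the SAP's printed list, add three that are missing, or restart its clock at a different procedure.

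**The denominator point is thin.** Agreed. Safety Subjects may well be defined in the full CIP, and no numerical difference from ITT is shown. It is a matter of alignment only.

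**The sizes are illustrative.** Also agreed. The shifts are assumed and held fixed whatever the observed count. Because the SAP keeps all ITT subjects in the denominator and 10 of its 12 components are 7-day events, n=180 fits its rule better than n=153. The n=153 row only follows the synopsis's own loss allowance.

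**Reusing 9% and 17% is not in itself an error.** True. The justification may lie in the CIP, so confirmation is the first request.

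**Conclusion.** The concern holds. The SAP supplied does not identify itself as the SAP for FARA-FREEDOM. If it is used for this trial, its primary safety composite differs from the synopsis in one added component, three omitted components and the procedure that starts the 7-day clock. It cannot be programmed as printed and be relied on to give the synopsis endpoint.

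The net effect on the event count is unknown in size and direction. At the decision boundary a single subject suffices. At n=180, a true rate of 9% and assumed net shifts of one or three subjects, the chance of a reversed conclusion is 6.0% or 22.3% from pass to fail and 4.5% or 9.9% from fail to pass. The sample size of 150 is arithmetically correct; that its 9% and 17% apply to the current composite is not shown. This should be settled before the primary safety analysis is programmed.

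**What to change.** 1. State whether FARA-FREE II is this study, and issue a final SAP that names FARA-FREEDOM and cites the current CIP revision.
2. In SAP 2.1.1 and 3.4.1, print the current protocol's component list, the procedures that start the 7-day clock, the late-onset window, the adjudicating committee and the analysis set. Printing the list once and referring to it from the other section avoids a second divergence.
3. Define Safety Subjects and state how that set relates to ITT.
4. Confirm, with the source, that the 9% planning rate and 17% goal apply to that composite.

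Items 1 to 3 cost SAP wording and programming only. Item 4 costs little if the justification exists; if it does not, the goal and the sample-size rationale must be re-derived.

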2.1.2 Additional Safety Endpoints

The proportion of subjects:

- 1. With any adverse event in the Composite Safety Endpoint definitions table, whether or not adjudicated as an SAE
- 2. With a device- or procedure-related SAE
- 3. With a device- or procedure-related stroke or TIA
- 4. With a pre-post cranial MRI change (brain imaging subpopulation)
- 5. Requiring cardioversion
- 6. Requiring an arrhythmia-related hospitalization
- 7. Learning curve analysis.

2.1.4 Additional Effectiveness Outcomes

- Acute Procedural Success, defined as the percutaneous endocardial creation of an electrically
 isolating set of lesions around the ostia of pulmonary veins (PV) during the index procedure, as
 clinically assessed by entrance and/or exit block performed ≥ 20 minutes after the last PVI lesion is
 made on a per patient basis.
- 2. The primary effectiveness endpoint for subjects not on AFDs between Day 105 and the 12 month follow-up visit.
- 3. First pass isolation (index procedure) consisting of Acute Procedural Success after a single planned set of lesions in each attempted PV
- 4. The proportion of subjects with early recurrence of atrial fibrillation (ERAF) by 90 days after the initial study ablation
- 5. The proportion of attempted subjects that achieve Acute CTI Success, defined as the creation of bidirectional electrical block across the cavo-tricuspid isthmus using the investigational devices.
- 6. Learning curve analysis
- 7. Rate of any reablation through 12 months of follow-up

3 Statistical Analyses

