CS1170 Rev D Clinical Study Synopsis

FARA-FREEDOM: A Prospective Open-Label Single Arm Post Market Clinical Follow-Up Trial of the FARAPULSE Pulsed Field Ablation System in Patients with Paroxysmal Atrial Fibrillation

SPONSOR: FARAPULSE, INC. [name]

ISSUE DATE: 18MAY 2022

This study is to be performed in accordance with Good Clinical Practice (GCP), the ethical principles that have their origin in the Declaration of Helsinki, International Conference on Harmonisation E6 and ANSI / AAMI / ISO Standards 14155:2020.

This document contains confidential and proprietary information and may not be copied or reproduced in whole or in part without the express written permission of FARAPULSE, INC., MENLO PARK, CA.

CONFIDENTIAL

© 2022, Farapulse, Inc.

MAY 18, 2022 PAGE 2

Revision History

Rev	DCO	Description of Changes	Effective Date	Prepared By		
В	21-289	To match the updated protocol	18Aug2021	[name]		
В	21-302	Administrative changes: Deleted "in either the Pulsed Field or Thermal Groups" In section 5.2 Index Procedure, Pg #4 which was inadvertently missed during the review of the document. Formatted document throughout to have same font and size for consistency.	27 Aug 2021	[name]		
C	21-323	Aligning with the protocol change	19Sep2021	[name]		
D	22-126	Aligning with the protocol change Page #3: Update to reflect the increase in total sites from 15 to 25 Page #11: CT was added as approved procedure to exclude presence of LAA thrombus	18 May 2022	[name]		

Executive Summary

SPONSOR NAME:	FARAPULSE, Inc.					
TITLE OF STUDY:	A Prospective Open-Label Single Arm Post Market Clinical Follow-Up Trial of the FARAPULSE Pulsed Field Ablation System in Patients with Paroxysmal Atrial Fibrillation					
REFERENCE CIP NUMBER / REVISION:	CS1169 Rev D					
Objective:	The purpose of the study is to provide ongoing post-market demonstration of the safety and performance of the FARAPULSE Pulsed Field Ablation System in the treatment of patients with paroxysmal atrial fibrillation (PAF).					
NAME OF	FARAPULSE Pulsed Field Ablation System					
INVESTIGATIONAL DEVICE:	 FARAWAVE[™] Pulsed Field Ablation Catheter FARASTAR[™] Pulsed Field Ablation Generator FARADRIVE[™] Steerable Sheath 					

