DESIGN:	Subjects will undergo percutaneous endocardial ablation for pulmonary vein isolation using the FARAPULSE Pulsed Field Ablation System. Subjects with typical right-sided (isthmus- dependent) atrial flutter (AFL) may undergo ablative interruption of the cavo-tricuspid isthmus (CTI). Class I / III antiarrhythmic drugs (AADs) will be discontinued at Day 60 ± 10 , subject to Investigator discretion Subjects will then be followed at 7 days, 30 days, 90 days, 6 months, and 12 months for adverse events (AEs), : Subjects will be monitored with weekly scheduled plus symptom-driven event monitoring, as well as 6 and 12-month Holter monitoring, for freedom from recurrent arrhythmia (atrial fibrillation [AF], AFL or atrial tachycardia [AT]) after the Blanking Period (Days 0 - 90).					
STUDY POPULATION:	Subjects with documented PAF who have had ≥ 2 episodes within 6 months of enrollment.					
Planned Enrollment:	180 subjects					
CLINICAL SITES:	Up to 25 enrolling centers.					

DURATION OF SUBJECT PARTICIPATION:	The enrollment period is estimated to take 12 months and subjects will be followed for up to 13 months. There will be a 3-month period of site close-out visits, for a planned study duration of approximately 34 months Coronavirus Disease 2019 (COVID 19)-related disruptions may alter this timeframe . Subject participation is anticipated to be 13 ± 1 months to allow for screening, pre-procedural diagnostic procedures, treatment and 12 ± 1 months of study follow-up.					

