PLANNED PROCEDURES:	 Index Procedure / Rescheduled Index Procedure: All subjects will be screened for atrial thrombus just prior to or at the time of the Index Procedure and will be rescheduled if positive. PVI: Subjects will undergo an attempt to isolate all pulmonary veins or their anatomic equivalent with the FARAPULSE Pulsed Field Ablation System. CTI: Subjects with a past history of CTI-mediated (typical) AFL, who manifest typical AFL during a procedure or within the Blanking Period, or who have inducible typical flutter, may undergo ablation of the CTI at the discretion of the Investigator using any approved RF catheter during the Index / Rescheduled Index Procedure or any reablation procedure. Other Ablation: Other ablation is not permitted under this protocol except when the Investigator determines that subject welfare requires ablation for an accessory pathway, atrioventricular nodal reentrant tachycardia (AVNRT), treatment-emergent left-sided AFL or incessant AT. 					
RE-ABLATION PROCEDURE	Re-ablation under this protocol requires documentation of Detectable AF, AFL or AT.Any re-ablation procedure for AF, AFL or AT during study follow-up constitutes a Treatment Failure.However, CTI ablation or re-ablation for right-sided typical AFL may be performed at any time during study follow-up and does not constitute a Treatment Failure.					

ANTIARRHYTHMIC DRUGS	 Antiarrhythmic drugs (AADs), except for amiodarone, may be utilized during the Blanking Period at the Investigator's discretion. On Day 60 ± 10 each subject will be contacted by telephone to stop all AADs. Class I / III AADs should be stopped at the Day 60 Assessment. However, at the Investigator's discretion, Class I / III AADs may be continued up to Day 90 without creating a primary performance endpoint failure. The use of amiodarone at any time during the study, except intraprocedurally to control an arrhythmia, or the use of Class I / III AADs after Day 90, constitute a Treatment Failure. 					

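### SAP 2.1.4 item 5 counts CTI block only if made with the investigational devices, but the protocol describes CTI ablation with RF catheters, so the outcome as written is 0% or undefined

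*SAP*

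**What the plan says.** SAP 2.1.4, item 5, plans to report "The proportion of attempted subjects that achieve Acute CTI Success". Success means "bidirectional electrical block across the cavo-tricuspid isthmus using the investigational devices", so the device is part of the success criterion. Item 5 does not say whether an attempt must also have been made with those devices to enter the denominator.

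The protocol synopsis, under Name of Investigational Device, lists three components of the FARAPULSE system: the "FARAWAVE[™] Pulsed Field Ablation Catheter", a pulsed field generator, and the "FARADRIVE[™] Steerable Sheath". Under Planned Procedures, the PVI entry has the operator attempt to "isolate all pulmonary veins or their anatomic equivalent with the FARAPULSE Pulsed Field Ablation System". The CTI entry says that subjects with typical flutter "may undergo ablation of the CTI at the discretion of the Investigator using any approved RF catheter", at the index, rescheduled index or any re-ablation procedure.

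The protocol's Additional Effectiveness Analyses do not include Acute CTI Success. The nearest entry is Treatment Success restricted to PVI and CTI ablation. The Schedule of Event does include a post-procedure assessment of CTI ablation, at index and re-ablation procedures.

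**The concern.** The success criterion and the described procedure do not meet. A subject whose CTI line is made with an RF catheter, and in whom bidirectional block is confirmed, has not had that block created by any listed investigational device.

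An analyst programming item 5 must then choose. Applying the words gives a table that carries no information on whether CTI block was achieved. Ignoring the device phrase gives an RF result under a definition that credits the study device. The second outcome matters because the study's stated purpose is to show the safety and performance of the FARAPULSE system.

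**Working it through.** The documents give no expected CTI success rate, number of CTI attempts or sample size for this outcome, so there is no planned figure to reproduce. The check applies the SAP definition to CTI ablation done as the protocol describes.

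**Inputs**
- Success criterion: bidirectional block created with the investigational devices (SAP 2.1.4, item 5).
- Investigational devices: pulsed field catheter, pulsed field generator, steerable sheath (protocol, Name of Investigational Device).
- Catheter described for CTI ablation: any approved RF catheter (protocol, Planned Procedures, CTI).
- Number of subjects with a CTI attempt: *m*, not given. CTI ablation is optional, so *m* is some subset of the planned 180.

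**Step 1: numerator.** If all CTI ablation follows the protocol's description, no block is created with a listed energy-delivering device. Successes = 0, whatever the true block rate.

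**Step 2: denominator.** There are two readings of attempted subjects.
- All subjects with a CTI attempt: 0/*m* = 0% for every *m* > 0.
- Only subjects in whom the investigational devices were used for the attempt: 0/0, undefined. Nothing is reported and no subject is misclassified.

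**Step 3: illustration under the first reading.** The *m* and block rates are assumed, not taken from the documents.

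| Assumed *m* | Assumed subjects with block | Literal item 5 | Without the device condition |
|---|---|---|---|
| 20 | 18 to 20 | 0/20 = 0% | 90% to 100% |
| 40 | 36 to 40 | 0/40 = 0% | 90% to 100% |

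SAP 3.1.1 allows a Clopper-Pearson interval for categorical outcomes. With zero successes the two-sided 95% upper limit is 1 − 0.025^(1/*m*). This is 16.8% at *m* = 20 and 8.8% at *m* = 40, so the interval would exclude the assumed block rates.

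**Step 4: what depends on item 5.** It has no performance goal, hypothesis or sample size. SAP 3.1.1 summarises categorical variables as counts and percentages. Item 5 is not a component of the primary safety or primary effectiveness endpoint in either document.

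**The case against.** The strongest reply is that this is one symptom of a larger mismatch. The SAP carries the FARA-FREE II name and predates the protocol revision by about 17 months. Its safety components, effectiveness definition and analysis set also differ from the synopsis. That probably explains the wording, but a new title page would leave item 5 unusable, so the definition itself has to change.

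A second reply is that the steerable sheath is an investigational device, so an RF catheter passed through it could be said to use the system. The sheath delivers no ablation energy and does not create block. At most this adds a third reading, in which success turns on which sheath was used.

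Third, a CTI lesion made with the pulsed field catheter would count. That is true, but it would fall outside the procedure the protocol describes.

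Fourth, the protocol document is a synopsis. The full investigational plan, to which the SAP defers for study details, was not available here and may define CTI success. This limits certainty about intent, but the conflict between the two texts remains.

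Two stronger inferences should be resisted. A reader might infer that every RF-treated CTI subject will be counted as a failure. That holds only with all CTI attempts as the denominator, which item 5 does not specify. A reader might also infer that the trial's main conclusions are at risk. They are not, because item 5 is one of seven additional outcomes and feeds neither primary endpoint.

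**Conclusion.** The definition is wrong as written for this protocol. Item 5 gives 0% or an undefined result, depending on how attempted subjects are read, and in neither case does it reflect whether block was achieved. This assumes only that CTI ablation is done as the protocol describes and that a sheath does not create block. The true block rate and the number of attempts do not matter.

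The consequence is confined to one descriptive outcome, which the protocol does not list. The primary endpoints, their tests and the sample size are unaffected. The risk is an uninformative zero, an empty row, or an RF result presented as study-device performance. It should be settled before analysis because the correction is small.

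**What to change.** Reconcile SAP 2.1.4 item 5 with the CTI entry under Planned Procedures in the protocol. Either of two edits does so.

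1. **Keep the outcome without the device condition.** Define it as bidirectional block among all subjects with attempted CTI ablation. State which procedures count, since the protocol allows CTI ablation at the index, rescheduled index and re-ablation procedures. Label the result as that of the CTI ablation performed, not as performance of the FARAPULSE system. Split it by catheter type only if the case report form records it.
2. **Delete item 5.** The protocol's Additional Effectiveness Analyses do not call for it, and SAP 3.5.1 would still describe CTI ablations among the lesion sets.

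Deletion costs one line. The first option is a short rewording and relies on the post-procedure CTI assessment already in the schedule. The sponsor should confirm that this assessment records bidirectional block, because the schedule does not say so. A split by catheter type is not shown to be free, because nothing supplied shows that catheter type is captured. Neither option says anything about which catheter should be used.
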